2.2 Study Endpoints

2.2.1 Primary endpoint(s)

Efficacy

- Objective response rate (ORR), defined as the proportion of patients whose best overall tumor response are confirmed complete response or partial response by RECIST 1.1.

2.2.2 Secondary endpoint(s)

Efficacy

- Duration of response (DOR), defined as the time from response criteria are first met for either complete response (CR) or partial response (PR), until the first date that

progressive disease (PD) is objectively documented, or until death (if death occurs within 9 weeks of the last evaluable scan), for subjects who achieve confirmed CR or PR.

- Progression-free survival (PFS), defined as the time from first dose of study treatment date to first documentation of objective progression or death due to any cause, whichever occurs first.
- Overall survival (OS), defined as the time from first dose of study treatment to death due to any cause.

Safety Endpoints

- Incidence of adverse events
- Deaths on study
- Discontinuations of study drug due to adverse events
- Changes in vital sign parameters
- Changes in hematology, chemistry, and other laboratory parameters
- ECG parameters
- ECOG performance status

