8.2 Analyses of Secondary Endpoints

8.2.1 PFS

Progression Free Survival (PFS) is defined as the time from the study treatment first dose to the earlier of disease progression or death due to any cause. Disease progression will be assessed using RECIST 1.1. The progression and censoring dates will be based on the May 2007 FDA Guidance for Industry, ‘*Clinical Trial Endpoints for the Approval of Cancer Drugs and Biologics*’. Determination rules for events or censored PFS is summarized in Table 2.

Table 2: Date of Event or Censoring for the Primary PFS analysis

Situation	Date of Event or Censoring	Outcome
Disease progression between scheduled disease assessments	Date of progression	Event
Death between scheduled disease assessment	Date of death	Event
Death before the first planned disease assessment at 6 weeks (plus 1 week window) without any disease assessment	Date of death	Event
No baseline disease assessments	Date of first dose	Censored
No post-baseline disease assessments without death before the first planned disease assessment	Date of first dose	Censored
Discontinuation of study treatment without progression (i.e., due to toxicity, withdrew consent, or lost to follow-up) and no further radiographic assessment ^a	Date of last radiological assessment	Censored
Alternate anticancer treatment started without documentation of disease progression beforehand ^b	Date of last radiological assessment prior to start of further anticancer treatment	Censored
Death or disease progression after missing two or more consecutively scheduled disease assessments ^c	Date of last radiological assessment without documented progression disease prior to death/progression	Censored
Patients who have not progressed and are alive	Date of last radiological assessment without documented progression disease	Censored

- For a patient who discontinues study treatment without PD and continues to have radiographic assessments, post-treatment radiographic assessments will be considered for PFS analyses according to the rules in this table.
- Alternate anticancer treatment interventions that are diagnostic (e.g. biopsy) or palliative (e.g., local radiation for painful nodule), as determined by medical review, will not routinely require censoring unless they are determined to interfere with the assessment of the patients’ disease status.

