- Disease assessments are planned every 6 (± 1) weeks for the first 6 months (24 weeks); and every 9 (± 2) weeks, thereafter, until disease progression. The interval of two missed scheduled assessments is calculated according to the

Situation	Date of Event or Censoring	Outcome
scheduled assessment frequency and the corresponding window (1 or 2 weeks depending on assessments scheduled before or after 6 months).		

PFS will be summarized descriptively using the Kaplan-Meier method. Median PFS and its corresponding 95% confidence interval will be reported. Greenwood's formula will be used to calculate the standard errors of the Kaplan-Meier estimate and upper and lower limits of the 95% confidence interval.

The PFS rate and its corresponding 95% confidence interval for various landmark time points (i.e., 6 months and 1 year) will also be estimated using the Kaplan-Meier method. The Kaplan-Meier curve of PFS will be provided.

Subgroup analyses for PFS will be performed, Kaplan-Meier curves and a forest plot will be presented.

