8.2.2 Duration of response (DOR) and disease control rate (DCR)

Duration of Response (DOR) will be calculated for subjects who achieve confirmed CR or PR. For such subjects, DOR is defined as the time from response criteria are first met for either CR or PR, until the first date PD is objectively documented, or until death. DOR will be right-censored based on the same rules as described for PFS above.

DOR will be summarized descriptively and the median DOR will be estimated using the Kaplan-Meier method.

Swimmer plots will be provided depicting graphically the duration of response for patients who achieve complete response or partial response per RECIST 1.1 in each cohort. For Cohorts 2 and 3, swimmer plots of tumor response will also be provided per irRECIST criteria.

Disease control rate (DCR) is defined as the proportion of evaluable subjects who achieved BOR of CR or PR with any duration or SD with duration of at least 3 months (i.e., ≥ 3 months). The estimate of the DCR will be accompanied by one-sided and two-sided 95% Clopper-Pearson confidence intervals. Additionally, DOR and DCR will be derived and summarized based on the irRECIST criteria for Cohorts 2 and 3 subjects.

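### SAP 2.2.2 and 8.2.2 count death as a DOR event differently, and after week 24 the 9-week limit in 2.2.2 is shorter than an allowed scan gap

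*SAP*

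**What the plan says.** **SAP 2.2.2 (endpoint list).** DOR runs from first meeting response criteria, for a confirmed response, to documented PD, "or until death (if death occurs within 9 weeks of the last evaluable scan"). It does not say how a later death is handled or on what date it would be censored.

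**SAP 8.2.2 (analysis section).** DOR runs "until the first date PD is objectively documented, or until death", with no time limit. It adds: "DOR will be right-censored based on the same rules as described for PFS above".

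**SAP 8.2.1, Table 2 (the PFS rules).** "Death between scheduled disease assessment" is an event on the date of death. "Death or disease progression after missing two or more consecutively scheduled disease assessments" is censored at the last scan. Two other rows censor at the last scan: "Alternate anticancer treatment started without documentation of disease progression beforehand", and "Discontinuation of study treatment without progression (i.e., due to toxicity, withdrew consent, or lost to follow-up) and no further radiographic assessment". No row contains a 9-week limit.

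**Scan schedule.** Table 2 footnote c plans scans every 6 (±1) "weeks for the first 6 months (24 weeks); and every 9" (±2) weeks after that. The SAP and protocol schedules count visits from the first dose of glembatumumab vedotin, so windows do not reset after an early or late scan.

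**Protocol 11.5.1.** DOR ends at documented recurrence or progression. Death is not named, there is no 9-week limit, and censoring follows the PFS conventions.

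**The concern.** One endpoint has two rules for when a death stops counting: a fixed 9 weeks after the last scan, or two consecutive missed visits. A programmer working from 2.2.2 and one working from 8.2.2 can build different DOR datasets from the same patients, and the same death can be a PFS event without being a DOR event.

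The 9 weeks equals the nominal interval after week 24 but ignores the ±2-week window. A fully compliant patient can therefore fall outside it. The ambiguity also carries into the irRECIST version of DOR that 8.2.2 plans for Cohorts 2 and 3. Responder numbers will be small: Cohort 1 rejects its null hypothesis at 6 responses, and SAP Section 3 illustrates 7, 8 or 9 for Cohorts 2 and 3. If the rule is chosen after the deaths are known, the choice is open to question.

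**Working it through.** **Inputs.** Visit weeks from first dose are 6, 12, 18 and 24, each ±1; then 33, 42, 51 and so on, each ±2 (Table 2 footnote c). The 9 weeks in 2.2.2 is a definition, so there is no planned calculation to reproduce.

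**Step 1. Longest gap with no scan missed** = (next visit + its window) − (date of previous scan), in weeks.

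| Visits | Previous scan on time | Previous scan as early as allowed |
|---|---|---|
| 18 to 24 (same for other 6-weekly pairs) | 25 − 18 = 7 | 25 − 17 = 8 |
| 24 to 33 | 35 − 24 = 11 | 35 − 23 = 12 |
| 33 to 42, and later pairs | 44 − 33 = 11 | 44 − 31 = 13 |

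In the 6-weekly phase the gap stays under 9 weeks, so a conflict there needs a missed scan. After week 24 it does not.

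**Step 2. One patient.** Scan at week 33, death at week 43, so 10 weeks later. The week-42 window runs from week 40 to week 44, so no visit has been missed. Assume no PD, no new anticancer therapy, and no treatment stop for a reason in Table 2's discontinuation row.
- Table 2: death between assessments, so a PFS event.
- SAP 8.2.2: a DOR event.
- SAP 2.2.2: 10 > 9, so not a DOR event.

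**Step 3. How far the two rules differ.** They part at 9 weeks after the last scan and meet again at the missed-visit limit. Footnote c does not fix that limit exactly. Taking it as the close of the second missed visit's window:

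| Last scan | Missed | Window closes | Late scan | On-time scan | Early scan |
|---|---|---|---|---|---|
| 6 | 12, 18 | 19 | 19 − 7 = 12 | 19 − 6 = 13 | 19 − 5 = 14 |
| 12 | 18, 24 | 25 | 25 − 13 = 12 | 25 − 12 = 13 | 25 − 11 = 14 |
| 18 | 24, 33 | 35 | 35 − 19 = 16 | 35 − 18 = 17 | 35 − 17 = 18 |
| 24 | 33, 42 | 44 | 44 − 25 = 19 | 44 − 24 = 20 | 44 − 23 = 21 |
| 33 (later visits alike) | 42, 51 | 53 | 53 − 35 = 18 | 53 − 33 = 20 | 53 − 31 = 22 |

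Another reading, twice the interval plus window, gives 2 × (6 + 1) = 14 and 2 × (9 + 2) = 22 weeks. Every value exceeds 9.

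**Step 4. What one death can do (invented data).** Seven responders all first respond at week 6. Six progress at weeks 18, 18, 24, 51, 60 and 69, so their DOR is 12, 12, 18, 45, 54 and 63 weeks. The seventh is the Step 2 patient, with DOR to death 43 − 6 = 37 weeks.
- Under 8.2.2 there are 7 events. S(12) = 5/7 = 0.71, S(18) = 4/7 = 0.57, S(37) = 3/7 = 0.43. The median is 37 weeks and S(40) = 0.43.
- Under 2.2.2 there are 6 events. S(18) = 0.57, then S(45) = 0.571 × 2/3 = 0.38. The median is 45 weeks and S(40) = 0.57. Because 2.2.2 gives no censoring date, this was done with censoring at the last scan (33 − 6 = 27 weeks) and at death (37 weeks). Both give the same median and S(40).
- If the fourth ending is instead a PD at week 42 (DOR 36) and the death is the fifth, sixth or seventh, the median is 36 weeks under both rules.

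**The case against.** The strongest reply is that this is a leftover phrase and not an open choice. Section 2.2.2 is only the endpoint list. Section 8.2.2 is the analysis section, carries the censoring instruction, and agrees with the protocol's use of the PFS conventions. A programmer would ordinarily follow 8.2.2. On exact nominal scan dates with none missed, a death before the next scan always falls within 9 weeks. DOR is descriptive, and SAP 5.2 treats the study as exploratory with no multiplicity adjustment.

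Most of this stands. It identifies the 2.2.2 parenthesis as the outlier and keeps the point small. It does not remove the contradiction: the supplied SAP text gives neither section precedence, and SAP Section 12 records only the retirement of the term ITT Population.

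A reader might go further in three ways that the documents do not support:
- **That every responder who dies without PD more than 9 weeks after a scan is affected.** Patients who started new therapy, or who stopped treatment for a reason in the discontinuation row and had no later scan, may be censored under both definitions.
- **That the sponsor has no rule settling the matter.** SAP Section 14, on shells and programming specifications, appears only as a heading in the supplied text, so its content cannot be ruled in or out.
- **That median DOR will shift.** Step 4 moves the median only because the death is the fourth of seven endings, where the curve crosses one half.

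**Conclusion.** The inconsistency is real and should be settled before DOR is programmed, but its reach is narrow. It concerns confirmed responders with no documented PD, no new anticancer therapy, and no treatment stop under Table 2's discontinuation row, who die more than 9 weeks after the last scan and before the missed-visit limit. Under the window-close reading of footnote c, that limit is 12–14 weeks for a last scan at week 6 or 12, 16–18 at week 18, 19–21 at week 24, and 18–22 from week 33 on. After week 24 the conflict can arise with no scan missed.

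The primary ORR test and the sample size are unaffected. The documents do not allow an estimate of how many responders would meet these conditions. One such death changes the event count and may change the median.

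**What to change.** 1. Delete the 9-week parenthesis from SAP 2.2.2.
2. Use one definition in 2.2.2 and 8.2.2: from the date response criteria are first met, for a confirmed response, to documented PD or death from any cause, censored by the Table 2 PFS rules.
3. Record in SAP Section 12 that death is counted as a DOR event, because protocol 11.5.1 does not name it.

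The cost is a small text change with no new data. Protocol Section 11 lets the SAP modify the protocol's plans and calls for an amendment only for major changes to the primary endpoint or its analysis, so none is needed. The downside is that reported DOR may be slightly shorter if a responder's late death becomes an event.

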2.2.3 Exploratory endpoint(s)

Efficacy

- Immune-related RECIST ORR and PFS (Cohorts 2 and 3)

Correlative:

- Concentration of antibody-drug conjugate(ADC), total antibody (TA), and free Monomethyl auristatin E (MMAE).
- Pharmacodynamic parameters, including gpNMB expression levels and other biomarkers in serum and both normal and tumor tissue; localization of glebatumumab vedotin, CR011, or MMAE at the tumor site; evaluation of tumor infiltrating and peripheral leukocytes, circulating tumor cells, and other immune response cells of interest. Additional analysis may include immune response assessment to potentially relevant tumor antigens.

3 DETERMINATION OF SAMPLE SIZE

Three cohorts of patients will be enrolled and treated. In Cohort 1, approximately 52 evaluable patients may be enrolled and treated with glebatumumab vedotin monotherapy with objective response rate (ORR) as the primary endpoint. As patients who discontinue study prior to the first disease assessment without symptomatic deterioration or death will not be evaluated and will be replaced, it is anticipated that approximately 60 patients will be enrolled in this cohort.

For Cohort 1, the sample size was determined to estimate the ORR with one-sided significance level of 5% and power of 80%, using exact binomial test, to determine if the ORR exceeds a predefined minimum. A sample size of 52 patients will test the null hypothesis of an ORR of 5% versus 15% under the alternative hypothesis. If the number of responses (CR or PR) is 6 or more, the null hypothesis will be rejected with the actual error rate of 0.045. If the number of responses is 5 or less, the alternative hypothesis will be rejected with an actual error rate of 0.188.

For Cohorts 2 and 3, ORR by RECIST 1.1 remains the primary endpoint. Supplementary analyses of tumor response and progression may also be performed using irRECIST criteria (in which new lesions do not necessarily constitute progression, but contribute to the calculated sum of diameter of all measurable disease) (Nishino, Giobbie-Hurder et al. 2013).

For Cohorts 2 and 3, 30 patients per cohort, to achieve 25 evaluable, will be enrolled to have the maximum width of the 95% confidence interval (CI) of the estimated ORR to be no greater than 41%. If 7, 8, or 9 responses are observed (i.e., the estimated ORR is 28%, 32%, or 36%) among the 25 evaluable patients, then the lower limits of the two-sided 95% CIs of the estimated ORR are 12%, 15%, and 18% respectively. These calculations are based on the Clopper-Pearson method for exact confidence intervals. As a secondary consideration, 25 evaluable patients can achieve 90% power for ORR of 25% comparing to 5% and 79% power comparing to 10% ORR with 1-sided type I error of 0.1 based on exact binomial test. Patients in Cohorts 2 and 3 who experience an event determined to be a treatment-limiting toxicity will not be replaced and will be considered evaluable.

4 ANALYSIS POPULATIONS

The three treatment cohorts will be analyzed separately.

4.1 Safety Population

The safety population will include all patients who receive at least one dose of study treatment of glembatumumab vedotin or varlilumab or a PD-1 targeted CPI. A baseline measurement and at least one laboratory, vital sign, or other safety-related measurement obtained after at least one dose of study treatment may be required for inclusion in the analysis of a specific safety parameter. For each cohort, the safety population constitutes all treated patients and will be used for secondary analyses of ORR and all other endpoints. The safety population is equivalent to the ITT population defined in the protocol.

4.2 Response Evaluable Population

Response evaluable population includes subjects who have measurable disease at baseline and receive study treatment, and excludes subjects who discontinue study prior to the first disease assessment without symptomatic deterioration or death. Specifically, patients who discontinue study prior to the first disease assessment for reasons unrelated to study treatment (i.e., adverse events deemed unrelated to study treatment, withdrawal of consent, lost to follow-up, withdrawal due to administrative reasons, etc.) will be excluded from the response-evaluable population and may be replaced. Patients who discontinue study prior to the first disease assessment due to treatment-related adverse events, symptomatic deterioration (adverse events due to progression), or death will be included in the response evaluable population. The primary ORR analysis is based on evaluable population and the secondary analysis will be based on safety (treated) population.

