7.2.4. Withdrawals and Replacement of Patients

Every effort should be made within the bounds of safety and patient choice to have each patient complete the study. An explanation will be recorded for each patient taken off study treatment or discontinuing the study.

Patients who discontinue study prior to the first disease assessment for reasons unrelated to study treatment (i.e., adverse events deemed unrelated to study treatment, withdrawal of consent, lost to follow-up, withdrawal due to administrative reasons, etc.) will be excluded from the response-evaluable population and may be replaced. Patients who discontinue study prior to the first disease assessment due to treatment-related adverse events, symptomatic deterioration (adverse events due to progression), or death will be included in the response evaluable population.

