7.2.4.2. Discontinuation from Study

Reasons for patient removal from the study include:

- Request of the patient or the patient's legal representative (withdrawal of consent for the study follow-up)
- Patient lost to follow-up
 - A subject should be considered lost to follow up only after multiple efforts have been made to contact the subject to assess his/her health status after failure of the subject to attend scheduled visits. If after two documented phone calls the investigative site is still unable to contact the subject, a certified letter should be sent to his/her home for immediate response. If there is still no response, the subject is to be considered lost to follow up. A record of the subject being lost to follow up should be noted in the source documents along with the phone contacts and the returned certified mail (if sent back).

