11.2. Sample Size and Power Calculation

Five cohorts of patients will be studied. In Cohort 1, approximately 52 evaluable patients may be enrolled and treated with glembatumumab vedotin monotherapy with ORR as the primary endpoint. As patients who discontinue study prior to the first disease assessment for reasons unrelated to study treatment will be excluded from the response-evaluable population, it is anticipated that approximately 60 patients will be enrolled.

For Cohort 1, the sample size was determined to estimate the ORR with one-sided significance level of 5% and power of 80%, using exact binomial test, to determine if the ORR exceeds a predefined minimum. A sample size of 52 evaluable patients will help test the null hypothesis of an ORR of 5% versus 15% under the alternative hypothesis. If the number of responses (CR or PR) is 6 or more, the null hypothesis will be rejected with the actual error rate of 0.045. If the number of responses is 5 or less, the alternative hypothesis will be rejected with an actual error rate of 0.188.

For Cohorts 2, 3, and 5, approximately 30 patients per cohort, to achieve 25 evaluable, will be enrolled to have the maximum width of the 95% confidence interval (CI) of the estimated ORR to be no greater than 41%. If 7, 8, or 9 responses are observed (i.e., the estimated ORR is 28%, 32%, 36%) among the 25 evaluable patients, then the lower limits of the two-sided 95% CIs of the estimated ORR are 12%, 15%, and 18% respectively. These calculations are based on the Clopper-Pearson method for exact confidence intervals. As a secondary consideration, 25 evaluable patients can achieve 90% power for ORR of 25% comparing to 5% and 79% power comparing to 10% ORR with 1-sided type I error of 0.1 based on exact binomial test. Cohort 4 will enroll approximately 10-12 patients for safety and tolerability assessment of glembatumumab vedotin and CDX-301. Pre-study and on-treatment tumor biopsies will be analyzed for the effect of CDX-301 on the tumor microenvironment, including the effect on intratumoral dendritic cell populations. The anti-tumor activity will also be explored as a secondary endpoint.

Patients in Cohorts 2-5 who experience an event determined to be a treatment-limiting toxicity will not be replaced and will be considered evaluable.

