11.4. Analysis Populations

11.4.1. Efficacy Analysis

The five treatment cohorts will be analyzed separately. For each cohort, the response-evaluable population will be the basis for the primary analysis of ORR in this study. Patients who discontinue study prior to the first disease assessment for reasons unrelated to study treatment (i.e., adverse events deemed unrelated to study treatment, withdrawal of consent, lost to follow-

up, withdrawal due to administrative reasons, etc.) will be excluded from the response-evaluable population and may be replaced. Patients who discontinue study prior to the first disease assessment due to treatment-related adverse events, symptomatic deterioration (adverse events due to progression), or death will be included in the response evaluable population. Every effort will be made to ascertain outcomes for all enrolled patients, irrespective of early discontinuation of protocol therapy.

The Intention-to-Treat (ITT) population constitutes all treated patients and will be used for secondary analyses of ORR and all other endpoints.

A supportive analysis using the per-protocol population may be performed for the efficacy analysis. The per-protocol population excludes patients that experienced important deviations from the protocol that may substantially affect the results of the primary analysis. In addition, a baseline measurement and at least one follow-up measurement obtained after at least one dose of study treatment may be required for inclusion in the analysis of a specific efficacy parameter. The final determination on protocol violations, and thereby the composition of the per-protocol population, will be made prior to locking the clinical database and will be documented in the statistical analysis plan.

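### For Cohort 1, SAP Section 3 as worded drops early study leavers with treatment-related adverse events from the evaluable set; the protocol and the explicit sentences of SAP 4.2 keep them.

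*SAP*

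**What the plan says.** The rule on early leavers appears in two forms.

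- **SAP 3, Cohort 1 sample size:** patients who "discontinue study prior to the first disease assessment without symptomatic deterioration or death will not be evaluated and will be replaced". Only symptomatic deterioration or death keeps an early leaver in.
- **SAP 4.2, opening sentence:** the population "excludes subjects who discontinue study prior to the first disease assessment without symptomatic deterioration or death". This is the same two-item test.
- **SAP 4.2, next sentence (opening with the word Specifically):** patients who leave early for reasons unrelated to study treatment "will be excluded from the response-evaluable population and may be replaced".
- **SAP 4.2, third sentence:** those who leave "prior to the first disease assessment due to treatment-related adverse events, symptomatic deterioration (adverse events due to progression), or death will be included".
- **Protocol 11.2, the counterpart of SAP 3:** "patients who discontinue study prior to the first disease assessment for reasons unrelated to study treatment will be excluded from the response-evaluable population".
- **Protocol 7.2.4:** those who leave before the first assessment "due to treatment-related adverse events, symptomatic deterioration (adverse events due to progression), or death will be included in the response evaluable population". The synopsis, 7.1 and 11.4.1 have the same rule; 11.4.1 begins it "Patients who discontinue study prior to the first disease assessment due to treatment-related adverse events".

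SAP 8.1 bases the primary ORR on the evaluable population and counts not-evaluable or missing responses as non-responses. SAP 12 lists one change from the protocol, the retirement of the term ITT.

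**The concern.** The evaluable set is the denominator of the primary endpoint. A patient driven off study by drug toxicity before the first scan is a treatment failure. Removing that patient from the denominator raises the estimated response rate.

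The non-responder rule in SAP 8.1 does not repair this, because it acts only on patients already in the evaluable set. Cohort 1 also has no treatment-limiting-toxicity rule to keep such patients in; SAP 3 gives that protection to Cohorts 2 and 3 only. In addition, SAP 3 makes replacement mandatory where SAP 4.2 and the protocol make it optional.

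**Working it through.** **1. The wordings applied to one patient.** Take a Cohort 1 patient who leaves the study before the first disease assessment because of a treatment-related adverse event, alive and without symptomatic deterioration.

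| Text | Status of this patient |
|---|---|
| SAP 3 | Excluded, and must be replaced |
| SAP 4.2, opening sentence alone | Excluded |
| SAP 4.2, second sentence | Not in the excluded group (reason is related to treatment) |
| SAP 4.2, third sentence | Included |
| Protocol 11.2 | Not in the excluded group |
| Protocol synopsis, 7.1, 7.2.4, 11.4.1 | Included |

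Within SAP 4.2 the second and third sentences make the first one specific, so the section most naturally yields inclusion. SAP 3 has no such qualification. It is the only unqualified departure.

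**2. The plan's own figures.** Inputs from SAP 3 and protocol 11.2: N = 52 evaluable, null ORR 5%, alternative 15%, one-sided 5% level, rejection at 6 or more responses, exact binomial test.

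- Type I error: P(X ≥ 6 | N, 0.05) = 1 − Σ(j=0..5) C(N,j) 0.05^j 0.95^(N−j). At N = 52 this is 0.0445; the plan states 0.045.
- Type II error: P(X ≤ 5 | 52, 0.15) = 0.1881; the plan states 0.188.

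Both reproduce.

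**3. Illustration: k affected patients kept on top of 52.** The documents do not give k. Suppose the SAP 3 wording leaves 52 evaluable and the protocol wording adds k non-responders. With 6 responders:

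| k | N | ORR | One-sided p against 5% | Critical count |
|---|---|---|---|---|
| 0 | 52 | 6/52 = 11.5% | 0.0445 | 6 |
| 1 | 53 | 6/53 = 11.3% | 0.0482 | 6 |
| 2 | 54 | 6/54 = 11.1% | 0.0520 | 7 |

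One such patient changes no conclusion. Two would reverse a result of exactly 6 responders. The chance of exactly 6 responders among 52 is 0.030 at a true ORR of 5% and 0.131 at 15%. That covers only one of the conditions for a reversal; at least two affected patients are needed as well.

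**4. Illustration: k affected patients dropped from 52 without replacement.** With 6 responders, N = 51 gives 6/51 = 11.8% and p = 0.0411; N = 50 gives 6/50 = 12.0% and p = 0.0378. The critical count stays at 6, so the test rule does not move and only the estimate rises slightly.

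**The case against.** The strongest reply is that SAP 3 does not define the population. It explains why about 60 patients are enrolled to obtain 52. SAP 4.2 is the defining section, and its explicit sentences agree with the protocol. The SAP 3 sentence also looks like leftover text: the protocol's summary of changes says Amendment 4 defined the response-evaluable population for clarification, while the SAP still describes three cohorts and carries older protocol section numbers. That is an inference, but a reasonable one. It means the likely intent is clear; it does not make the SAP 3 sentence correct.

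The second reply is that almost nobody is affected. The rule concerns leaving the study, not stopping treatment. Protocol 7.2.4.1 has patients who stop treatment without progression continue their disease assessments. Protocol 7.2.4.2 gives only two reasons for removal from the study: a patient request ("withdrawal of consent for the study follow-up") and loss to follow-up. SAP 4.2 lists both consent withdrawal and loss to follow-up among its examples of excluded reasons. This stands, and it is why the point is minor.

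Third, the planned ORR on all treated patients is untouched by either wording. That is a real safeguard, but it is a secondary analysis.

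A reader might also extend the point to Cohorts 2 and 3. The documents do not support that from SAP 3: its sentence is tied to Cohort 1, and SAP 3 keeps patients with a treatment-limiting toxicity evaluable in the other two cohorts. In Cohort 3 that covers any treatment-related toxicity warranting discontinuation (protocol 8.7). In Cohort 2 some treatment-related events are not treatment-limiting toxicities, but an exclusion there would rest only on the opening clause of SAP 4.2, which the later sentences override.

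**Conclusion.** The SAP 3 sentence is wrong as written for Cohort 1. It conflicts with the protocol in five places (synopsis, 7.1, 7.2.4, 11.2, 11.4.1) and with the explicit inclusion in SAP 4.2, and it is not declared as a change. The opening clause of SAP 4.2 is the same leftover wording in a place where the following sentences already correct it.

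If the SAP 3 rule were applied, the bias in ORR would be upward. Its size is unknown because the number of affected patients is not in the documents; it is probably very small. A changed test result in the illustration needs at least two such patients on top of 52 and exactly 6 responders. If SAP 4.2 is followed as its explicit sentences read, there is no bias and the matter is one of wording.

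Two stronger readings are tempting. One is that the sponsor has chosen to exclude toxicity failures from the primary analysis; the explicit inclusion in SAP 4.2 contradicts that. The other is that the Cohort 1 type I error exceeds 5%. That would require an assumed number of affected patients and their replacement up to 52. The documents give no such number, and the protocol describes Cohort 1 enrolment in the past tense, so replacement may no longer apply. Severity: minor.

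**What to change.** - **SAP 3:** use the protocol 11.2 wording, so that only discontinuations for reasons unrelated to study treatment are excluded, and make replacement optional, as in SAP 4.2 and the protocol.
- **SAP 4.2:** delete the opening sentence's exclusion clause ("excludes subjects who discontinue study prior to the first disease assessment without symptomatic deterioration or death", with the joining word before it). The two sentences that follow then carry the rule alone.

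Patients who leave before the first scan because of treatment-related adverse events then stay in the denominator and count as non-responders under SAP 8.1.

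The cost is a wording change in two places in the SAP, with no new data and no protocol amendment. If the SAP 3 wording would otherwise have been applied, the reported Cohort 1 ORR may be slightly lower.
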